Patients eligible to receive TeleGRACE services include:

- Veterans discharged from the Indianapolis VA medical center (VAMC) for an medical/surgical diagnosis (excludes substance use disorder-related admissions; excludes planned admissions)
- Age ≥ 70 years
- Not enrolled in home-based primary care (HBPC)
- Not enrolled in hospice
- Not in dialysis
- Primary care visit within VA in the prior 2 years
- Not residing in nursing home, skilled nursing facility, or CLC
- CAN score $\geq 95^{\text{th}}$ percentile for mortality or missing CAN score
- Discharged from the hospital alive

Exclusion Criteria

- Patients who have been randomized to the control arm after their index hospitalization who become readmitted to the hospital may not be re-randomized.
- Enrolled in in-person GRACE
- Enrolled in home-based primary care (HBPC)
- Enrolled in hospice
- Enrolled in complex care program
- Dialysis (hemodialysis or peritoneal dialysis)
- Residing in nursing home, skilled nursing facility, or CLC
- Living >60 miles from the Indianapolis VAMC facility

Outcome Measures

The primary outcome for the TeleGRACE evaluation will be:

- 90-day all-cause mortality (measured as 90-days from discharge from the index hospital stay)

The secondary outcomes are:

- 90-day readmissions
- 1-year all-cause readmissions
- 1-year mortality
- 1-year ED utilization (VA and non-VA)
- 1-year falls

We will explore using time to nursing home placement as a secondary outcome. We have requested the data and will evaluate the data source for completeness; comparing it against chart review. If the team considers the data source to be accurate, then we will examine time to nursing home placement as a secondary analysis.

Randomization

Patients will be randomized in ratio of 1 (control):2 (intervention) stratified by site of primary care (Indianapolis VAMC versus non-Indianapolis [e.g., CBOCs]). We created a computer-generated randomization list (with random block sizes of 3 or 6) for each strata. With the current capacity

of VA GRACE program staff, our goal is to enroll 5 patients to TeleGRACE each month. The project will seek to enroll a total of 180 patients to TeleGRACE and 360 to usual care in a three-year recruitment period.

Data Sources

Corporate Data Warehouse (CDW) data

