CDW data will be used to assess patient baseline characteristics (e.g., age, demographics, past medical history, prior healthcare utilization) as well as outcomes (i.e., ED utilization, readmission, mortality, and falls). In this way, the same data source is used to identify outcomes for both intervention and control patients.

Chart Review data

Chart review will be used to validate the TeleGRACE dose classification that is based on CDW data (see Per-Protocol analysis described below).

Follow-up Period

Patients will be followed for one year from the date of discharge from their index hospitalization. Unlike clinical trials that require in-person outcome assessments and hence implement “windows” for data collection, this evaluation will use electronic health record data for outcome assessment and hence no windows will be specified.

ANALYSIS PLAN

Intention-to-Treat Analysis

We will compare baseline characteristics between TeleGRACE patients and control patients using chi-square tests for categorical data and t-tests for continuous characteristics.

In the primary intention-to-treat (ITT) analysis, we will compare outcomes between patients randomized to usual care and those to TeleGRACE adjusting for the baseline characteristics that are significantly different by logistic regression for the binary outcome and Poisson regression for count data. If the sample size is sufficient, we will examine the effect of the TeleGRACE program by site of receipt of primary care services.

Per-Protocol Analyses

Not all patients who are randomized to receive TeleGRACE will receive services from the TeleGRACE staff. This situation is anticipated for patients who decline GRACE and others who become ineligible after discharge from the index hospitalization but before their first virtual home visit post-discharge (e.g., patients who die, get readmitted, or move to a skilled nursing facility after discharge). In the exceptionally rare case, patients may be discharged from TeleGRACE due to safety concerns for our staff (e.g., sexually or physically aggressive behavior, unwillingness to cage animals, unwillingness to store firearms). The per-protocol analyses will be similar to the planned intention-to-treat analysis but will compare the outcomes between patients who received GRACE service versus patients in usual care.

Given the expected heterogeneity in the number of TeleGRACE visits, patients will be classified into four categories as follows:

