1. **Full TeleGRACE dose:** the patient received a virtual post-discharge transitional visit, followed by a virtual baseline visit with multidisciplinary team discussion, and then follow-up virtual discussion to ensure that the patient and caregiver agree with and understand the plan of care. These patients may receive additional follow-up contacts with the TeleGRACE/GRACE team members over the course of the one year follow-up period. Note: in the atypical situation where the patient did not receive a transitional visit but did receive a baseline assessment, the patient will still be classified as "full TeleGRACE dose").
2. **Transitional visit dose:** the patient received a virtual post-discharge transitional visit but did not receive a baseline visit. These patients may receive additional follow-up contacts (typically by telephone) with the TeleGRACE/GRACE team members over the course of the one-year follow-up period. In some cases, the patient may receive multiple transitional visits (e.g., after readmissions).
3. **Partial dose:** the patient received neither a post-discharge transitional visit nor a baseline visit but had other contact with the TeleGRACE/GRACE team (typically telephone visits).
4. **No TeleGRACE:** patients may have been contacted by the TeleGRACE/GRACE team in an attempt to schedule a visit, but these patients received no clinical visits or encounters. Patients who decline TeleGRACE services are included in this category. Please note: in a research randomized controlled trial, only patients who are potentially interested in participation are consented and then randomized. TeleGRACE is a quality improvement project, therefore enrollment follows procedures used in clinical care.

We will further examine the outcomes among patients across these 4 categories as well as the control patients.

Sensitivity Analyses

Considering the heterogeneity in the TeleGRACE patients, we plan to conduct the following sensitivity analyses

1. **Enrolled versus Randomized to TeleGRACE:** We will conduct the ITT analysis described above which compares patients *randomized* to TeleGRACE versus usual care controls. In addition, we will compare patients who *enrolled* in TeleGRACE versus control patients.
2. **Dose:** In addition to the description of TeleGRACE services as provided in the per-protocol analysis, the dose of the TeleGRACE program will be assessed in terms of:

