 - a. The total number of GRACE contacts (telephone, virtual or in-person) in the one-year post-discharge from the index event.
 - b. Typically, home visits are conducted by a dyad of a nurse practitioner and social worker. Given staffing constraints, some patients may only receive a visit by a social worker or a nurse practitioner but not both. Therefore, each transitional, baseline, and follow-up visit will be assessed to describe whether it was conducted by social work, nursing, or other staff.
 - c. A key element of the GRACE program is the development of a multidisciplinary plan via discussion at the weekly GRACE rounds. The number of times an individual patient is discussed by the entire team in the year post-discharge will

be recorded (the geriatrician's summary of the multidisciplinary discussion will be used to identify whether a patient was discussed during team rounds).

3. **Discontinuous Eligibility Periods:** Patients who become permanently ineligible for TeleGRACE (e.g., are readmitted and then subsequently discharged to a long-term care facility) will be censored on the date they became ineligible for the outcome measures because they became ineligible for services. However, this censoring plan will be implemented retrospectively because it is expected that the older persons who will be enrolled in this study may have intermittent periods of ineligibility (e.g., during a hospital stay and then followed by short-term rehabilitation stay). Such patients may still benefit from the intervention and hence will not be censored either from the intervention or control groups.
 - a. For all intervention patients, we will calculate the proportion of eligible days a patient is cared for by the GRACE team as: the number of days that the patient was under the care of the GRACE team divided by the total number of days the patient was potentially eligible for GRACE.
 - b. We will note whether the period of eligibility was either continuous or discontinuous.
 - c. For patients with a discontinuous eligibility period, we will describe the patterns of discontinuity. For example, some patients may have a short hospital stay early post-discharge but then receive a relatively long period of GRACE services in the year post-discharge. In contrast, other patients may have recurrent hospitalizations some of which may be followed by short-term rehab stays resulting in fragmented eligibility periods of relatively short durations.

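### TeleGRACE dose is classified from visits over the whole follow-up year, so early death lowers dose and higher dose would look protective even if the visits did nothing

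*Combined protocol and SAP*

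**What the plan says.** Per-Protocol Analyses sorts TeleGRACE patients into full dose, transitional visit dose, partial dose and no TeleGRACE, according to which visits or contacts they received. No deadline is set for the transitional or the baseline visit. The plan then states: "We will further examine the outcomes among patients across these 4 categories as well as the control patients".

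Sensitivity Analyses, item 2, adds that "the dose of the TeleGRACE program will be assessed in terms of" three further measures. Item 2a is "The total number of GRACE contacts (telephone, virtual or in-person) in the one-year post-discharge from the index event". Item 2c begins "The number of times an individual patient is discussed by the entire team in the year post-discharge will" and goes on to say that this number is recorded. Item 2b describes which staff made each visit.

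On timing, Outcome Measures gives the primary outcome as "90-day all-cause mortality (measured as 90-days from discharge from the index hospital stay", and the secondary outcomes run to 90 days or one year. Follow-up Period says: "Patients will be followed for one year from the date of discharge from their index hospitalization".

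Two passages link events to dose:

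- The transitional visit category notes: "In some cases, the patient may receive multiple transitional visits (e.g., after readmissions".
- Per-Protocol Analyses expects no service for "others who become ineligible after discharge from the index hospitalization but before their first virtual home visit post-discharge (e.g., patients who die, get readmitted", and item 3 of the sensitivity analyses describes temporary ineligibility during hospital and rehabilitation stays.

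No landmark, time-varying exposure or rate per day at risk is given for the categories or for items 2a and 2c. Item 3a is a separate measure. Item 3d changes the outcome models only if more than 10% of patients are censored, and it leaves the definition of dose as it is.

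**The concern.** A patient must live long enough to receive a visit. Someone who dies on day 10 can hardly reach the full-dose category or collect many contacts, whatever the visits achieve. Dose measured over an open window therefore contains information about survival, and comparing mortality by that dose partly compares survivors with the dead (immortal time bias). The control patients, who are part of the category comparison, had to survive to no visit at all.

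For readmissions, ED visits and falls the events can also change dose. A readmission may lead to another transitional visit, which raises dose. It may also come before the first visit or suspend eligibility, which lowers dose.

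The risk is that a survival gradient created by timing is reported as dose-response evidence for the program.

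**Working it through.** The point disputes no figure in the plan, so there is none to reproduce. The check asks what each dose measure would show if visits had no effect on outcomes.

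**Inputs from the plan.** 90-day mortality of 2% (TeleGRACE) and 8% (usual care) and 180 TeleGRACE patients, from Power. 8% is the rate TeleGRACE patients would have if the program did nothing. 2% is the projected rate, taken here with no further effect of dose within the arm.

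**Assumptions, because the plan gives no figures.** Constant death hazard. The baseline visit, which puts the patient in the full-dose category, falls at an exponential time with mean 21 or 45 days. 70% or 85% accept, regardless of prognosis. For the counts: 6 or 12 contacts per year while alive, 0.5 or 1 readmission per year, and 0%, 50% or 100% of readmissions adding one contact.

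**Step 1, windows.** 365 − 90 = 275 days, so 275/365 = 75% of the window in 2a and 2c lies after the primary outcome has closed.

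**Step 2, the four categories.** Let m be 90-day mortality, h = −ln(1 − m)/90, μ = 1/(mean visit day) and a = acceptance.

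- Death by day 90 before the visit would occur: A = h/(h + μ) × [1 − exp(−90(h + μ))]
- Visit before death: F = μ/(h + μ)
- Mortality in full dose: (m − A)/F
- Mortality in all others: [m − a(m − A)]/(1 − aF)

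Example with m = 0.08, mean day 45, a = 0.85: h = 0.000926, μ = 0.0222, A = 0.0350, F = 0.960. Full dose: 0.0450/0.960 = 4.7%. Others: 0.0418/0.184 = 22.7%. Ratio 4.85.

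| m | Mean visit day | Acceptance | Full dose | Others | Ratio |
|---|---|---|---|---|---|
| 2% | 21 | 70% | 1.5% | 3.1% | 1.97 |
| 2% | 21 | 85% | 1.5% | 4.5% | 2.92 |
| 2% | 45 | 70% | 1.1% | 3.9% | 3.44 |
| 2% | 45 | 85% | 1.1% | 6.5% | 5.72 |
| 8% | 21 | 70% | 6.2% | 11.9% | 1.90 |
| 8% | 21 | 85% | 6.2% | 16.9% | 2.70 |
| 8% | 45 | 70% | 4.7% | 14.8% | 3.16 |
| 8% | 45 | 85% | 4.7% | 22.7% | 4.85 |

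In the 8% rows the program does nothing, yet full-dose patients at 4.7% to 6.2% would compare favourably with controls at 8%.

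**Step 3, one-year contact count and mortality.** Patients who die by day 90 live about 45 days on average, so they collect about 6 × 45/365 = 0.74 or 12 × 45/365 = 1.48 routine contacts. In a simulation of 400,000 patients per scenario, the rest average 5.5–6.8 or 10.9–12.7. Mortality at or below the median count, against above it:

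- 90-day: 3.2–3.7% against 0.0% at the 2% rate; 13.6–16.1% against 0.0% at the 8% rate.
- One-year, with the same hazard continued: 11–13% against 1.5–2.1%; 44–50% against 7–10%.

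These ranges include scenarios in which no readmission adds a contact, so the gap comes from death ending accrual.

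**Step 4, contact count and readmissions, one-year survivors only.** With no readmission adding a contact, 0.50 against 0.50 readmissions. With 50–100% adding one, patients above the median have 1.25 to 1.90 times as many. These scenarios omit the contacts that a readmission can prevent.

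**Step 5, day-30 landmark.** Contacts are counted in days 0–30 and deaths in days 31–90 among patients alive at day 30. Low against high dose is then about 1.3% against 1.3–1.4% at the 2% rate, and 5.3–5.5% against 5.4–5.5% at the 8% rate, so the artefact is gone. With S(30) = (1 − m)^(1/3), the deaths left per 180 patients are 180 × (0.9933 − 0.98) = 2.4 and 180 × (0.9726 − 0.92) = 9.5.

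**The case against.** The strongest reply is that item 2 is descriptive. Its three measures are to be assessed, described and recorded, and no sentence links the contact or discussion count to an outcome. That stands: a reader might infer a planned model of outcomes on contact count, but the plan does not write one. The heading Sensitivity Analyses, in a document limited to effectiveness, leaves the intention open. The reply does not cover the four categories, whose outcome comparison is explicit.

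A second reply is that the categories depend on visit type, so repeat transitional visits move nobody up and a split on contact count says nothing about them. This is right, and it is why step 2 treats the categories separately. They are still biased, because reaching full dose requires surviving to the baseline visit.

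Third, a reader might infer that readmissions generate the contacts and so drive the whole problem, with more contacts bound to look harmful for readmissions. The documents do not support this. Extra transitional visits are mentioned only for some cases, while readmission can also prevent or suspend contact. The mortality artefact appears with no readmission-generated contacts at all.

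Finally, a landmark analysis keeps few deaths and does not remove confounding by health or willingness to take part. Both points stand, and they limit what any dose analysis here can show.

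**Conclusion.** The point holds for the comparison across the four categories, and for the counts in 2a and 2c if they are related to outcomes. Timing alone would produce 90-day mortality 1.9 to 5.7 times as high outside the full-dose category, under the assumed visit timing and acceptance. For the contact count it would produce a gap from 3.2–3.7% (at the 2% rate) or 13.6–16.1% (at the 8% rate) down to about zero. The sizes depend on those assumptions. The direction for mortality does not, since death always ends accrual. For readmissions, ED visits and falls, distortion is expected but its net direction cannot be fixed from the documents.

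It would be too strong to say that no dose–outcome relation could be interpreted. The problem lies in dose as now defined, and the timing part can be removed. The intention-to-treat primary analysis is unaffected. Because the outcome comparison is stated and the remedy is cheap, the plan should be changed.

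**What to change.** 1. For every dose–outcome comparison, classify dose from contacts up to a prespecified landmark and before any readmission. Day 30 is an example; choose the day from the program's usual visit timing, which the plan does not give. Compare only later outcomes, in patients alive at the landmark, and apply the same landmark to controls. A time-varying dose exposure is an alternative.
2. State that the one-year counts in 2a and 2c describe services delivered and will not be related to outcomes.
3. Label the dose results exploratory, and say that confounding by health and willingness remains. A readmission before the landmark also shortens the time to accrue dose, so report such readmissions by dose group.

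This is a change of wording, provided that contact and event dates are held in the data warehouse and charts already in use. The costs are real:

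- Events before the landmark drop out: with day 30, about 180 × (1 − 0.9933) = 1.2 to 180 × (1 − 0.9726) = 4.9 TeleGRACE deaths.
- About 2 to 9 deaths per 180 TeleGRACE patients remain in days 31–90, so mortality by dose will be imprecise.
- Later baseline visits no longer count. Under the timing assumed above, exp(−30/21) = 24% to exp(−30/45) = 51% of first baseline visits would fall after day 30.

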 - d. If there are more than 10% patients censored for the outcomes, we will conduct Cox-regression analysis for the hazard of death and risk-exposure adjusted Poisson regression for the number of readmissions and number of falls.

POWER

For **Aim 1** (effectiveness of TeleGRACE versus usual care), we expect to observe 2% and 8% 90-day all-cause mortality for the TeleGRACE and usual care patients, respectively. This projected effect size is conservative based on our propensity-score weighting analysis comparing GRACE patients with usual care patients. With 180 TeleGRACE and 360 usual care patients, the study has 0.96 power at detect the efficacy of TeleGRACE program with a one-sided normal test at a significance level 0.05. Considering a 10% drop-out, the analysis has 0.94 power to establish the TeleGRACE efficacy with the same effect size.

DATA MONITORING

Enrollment

We will closely monitor the randomization of TeleGRACE with the expected rate of 5 per month. We will plot the number of actual randomized patients and its expected number against the study time and update the figure on a monthly basis. Prior to the DSMB meeting, we will estimate the current randomization rate and project the final number of randomized patients by end of the fourth year with the current rate along with its 95% confidence interval based on the Poisson distribution. If the upper bound of the 95% interval is below the target number of 180. We will modify the enrollment strategy to ensure that we achieve the enrollment goal.

Interim Analysis

Since the observed effect size of in-person GRACE versus usual care is quite substantial with respect to 90-day all-cause mortality, we plan an interim analysis when a half of the enrolled patients can be evaluated for the primary outcome. One-sided normal testing will be applied for the interim analysis using O'Brien-Fleming group sequential test with the overall type error controlled at 0.05. The hypotheses are:

$$H_0: p_1 = p_2 \text{ vs. } H_1: p_1 < p_2,$$

where p_1 and p_2 stand for the 90-day all-cause mortality in TeleGRACE and usual care arms, respectively.

If the Z – test statistic crosses the boundary of -2.54 at the interim analysis, the trial will be recommended for stopping for efficacy; otherwise, the trial will continue to the end with the crossing boundary for the test statistic at -1.66. The overall power with the interim analysis for this study is 0.82.

Safety

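### Powers of 0.96 and 0.82 cannot both belong to one test at 180/360; the stopping Z and the arm sizes are unsettled, and two-look error at 8% mortality in both arms runs from 3.5% to 6.6% accordingly

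*Combined protocol and SAP*

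**What the plan says.** **Power section.** For 90-day mortality of 2% against 8%, with 180 TeleGRACE and 360 usual-care patients, "the study has 0.96 power at detect the efficacy of TeleGRACE program with a one-sided normal test at a significance level 0.05". With 10% drop-out the figure becomes 0.94.

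**Interim Analysis section.** There is one look, when half the patients can be evaluated, using a one-sided normal test and an O'Brien-Fleming "group sequential test with the overall type error controlled at 0.05". If the statistic "crosses the boundary of -2.54 at the interim analysis, the trial will be recommended for stopping for efficacy"; otherwise the final boundary is -1.66. The section ends: "The overall power with the interim analysis for this study is 0.82". No formula for Z is given.

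**Intention-to-Treat Analysis section.** The primary comparison is made "adjusting for the baseline characteristics that are significantly different by logistic regression for the binary outcome". It is not linked to the -1.66 boundary.

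**Randomization section.** "Patients will be randomized in ratio of 1 (control):2 (intervention", with the further statements "our goal is to enroll 5 patients to TeleGRACE each month" and "a total of 180 patients to TeleGRACE and 360 to usual care in a three-year recruitment period".

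**The concern.** The plan fixes the hypotheses, direction, timing and boundaries of the stopping rule, but not the statistic. With unequal arms and few deaths, the usual candidates (unpooled Z, pooled Z, logistic Wald) can disagree on the same table. The stopping recommendation could then rest on a choice made after the interim data are seen.

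The plan's own numbers do not settle the choice. A single early look with these boundaries should barely change power, yet the stated value falls from 0.96 to 0.82. The allocation ratio also conflicts with the arm sizes, and which arm is larger decides which statistic exceeds 0.05. At stake are the promised error rate, the meaning of an early stop, and the power on which the trial was justified.

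**Working it through.** **Inputs.** From Power and Interim Analysis: mortality 2% and 8%; arms 180/360 (162/324 after 10% drop-out); one-sided 0.05; boundaries -2.54 and -1.66; look at one half. Assumptions: the interim holds half of each arm, and no covariates are used, because the SAP gives no covariate data.

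**1. Reproducing 0.96 and 0.94.** Unpooled normal formula:
- 180/360: SE = sqrt(0.02×0.98/180 + 0.08×0.92/360) = 0.01770; 0.06/0.01770 = 3.390; Φ(3.390 − 1.645) = 0.9595.
- 162/324: SE = 0.01866; Φ(3.216 − 1.645) = 0.9419.

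Other formulas at the same arm sizes do not match both figures: pooled null SE with unpooled alternative SE 0.915/0.885, pooled throughout 0.869/0.837, arcsine 0.937/0.914, unpooled with continuity correction 0.934/0.907.

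**2. Cost of the look.** Treat the two Z values as bivariate normal with correlation sqrt(0.5). Under the null, the boundaries give overall error 0.0502, so they are right under normal theory. With final mean 3.390, power is 0.9587. The loss is 0.9595 − 0.9587 = 0.0008. Drop-out does not explain 0.82 either (two-look 0.941 at 162/324).

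**3. A candidate for 0.82.** Log-odds-ratio Wald statistic at 180/360:
- difference = ln(0.08/0.92) − ln(0.02/0.98) = 1.449
- SE = sqrt(1/(180×0.02×0.98) + 1/(360×0.08×0.92)) = sqrt(1/3.528 + 1/26.496) = 0.567
- ratio = 2.558; single-look power 0.819; two-look power 0.817

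This is the Wald statistic of a logistic model without covariates.

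**4. Allocation.** Five per month for 36 months is 180 TeleGRACE. At 1 control to 2 intervention that implies 90 controls. The stated 360 is 2 control to 1 intervention.

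**5. Exact two-look results.** All binomial tables at the interim are enumerated and convolved with the second half; reject at Z ≤ -2.54, then Z ≤ -1.66. Logistic Wald tables with zero deaths in an arm count as no rejection. Error is at 8% in both arms; power is at 2% against 8%.

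| TeleGRACE/usual care | Unpooled Z | Pooled Z | Unadjusted logistic Wald |
|---|---|---|---|
| 180/360 | 6.6% / 0.952 | 4.65% / 0.930 | 4.4% / 0.897 |
| 180/90 | 3.5% / 0.651 | 5.5% / 0.757 | 5.0% / 0.704 |

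Keeping the ratio and the total of 540 instead (360/180) gives unpooled 4.0% / 0.914 and pooled 5.3% / 0.943.

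For common mortality from 2% to 20% at 180/360, the unpooled error runs from 8.5% down to 5.8%, and the pooled error stays between 4.2% and 4.9%.

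**6. Interim decision.** At 90/180 under the planned effect, the chance of stopping is 48% unpooled, 21% pooled and 0.6% logistic Wald. The unpooled Z stops and the pooled Z does not with probability 27%. For example, 1/90 against 14/180 gives -2.92 unpooled (stop) and -2.25 pooled (continue).

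**The case against.** - **The plan does not say the unpooled Z will be used.** This stands. A planning formula does not fix the analysis statistic. Nor is the match in step 1 unique once the arms are in doubt: with 360 TeleGRACE and 180 usual care, the pooled-throughout formula gives 0.956/0.938, which also rounds to 0.96/0.94. A reader might infer that the trial's true error is 6.6%. The documents do not support that: it needs an unpooled variance, TeleGRACE as the smaller arm, and 8% mortality in both arms.
- **The 0.82 may be no arithmetic error.** This stands too. Step 3 reaches it from the plan's named model type, arms and boundaries. A reader might infer that 0.82 is simply wrong or has no traceable source; neither follows. What remains is that two powers are given as if for one test.
- **The disagreement between variances matters mainly at the interim.** Largely true. Stopping is only recommended there, and overall power differs by about 2 points (0.952 against 0.930). The table nearest the planned rates (expected deaths 1.8 and 14.4) is 2/90 against 14/180, which gives -2.20 unpooled and -1.82 pooled, so both continue. The 1/90 table shows that the choice can matter, not what the plan expects.
- **Normal-theory boundaries are always approximate.** Accepted, and these are correct on that basis. But the approximation error differs by statistic and changes direction with the allocation, so the statistic has to be named.

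**Conclusion.** The concern holds in three parts.

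1. The stated 0.96/0.94 and 0.82 cannot all be the power of one test at 180/360, since the look costs under 0.1 point. They may rest on two different statistics; neither origin is proven.
2. The 1 control to 2 intervention ratio contradicts 180 TeleGRACE and 360 usual care. The documents do not show which is intended. This conflict has the largest effect on power: about 0.90 to 0.95 at 180/360, but 0.65 to 0.76 at 180/90, depending on the statistic.
3. Whether the promised 0.05 holds depends on the undefined Z and on the arms. At 8% mortality in both arms the exact error runs from 3.5% to 6.6% over the cases tabulated. The unpooled Z exceeds 0.05 at 180/360 and the pooled Z exceeds it at 180/90.

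These results assume half of each arm at the interim and no covariate adjustment. The logistic figures also depend on how zero-death tables are handled.

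**What to change.** 1. Reconcile the allocation ratio in the Randomization section with the 180/360 stated there and in Power.
2. Name one test, with its variance, for both looks, and say whether that test or the adjusted logistic model is confirmatory at -1.66. If 180/360 is confirmed, the pooled (score) Z with the existing boundaries keeps the error at or below 0.05 at the mortality rates examined (2% to 20%). If TeleGRACE is the larger arm, the pooled Z slightly exceeds 0.05 at the planned 8% mortality, and the error of the chosen test should be checked by exact enumeration.
3. Replace 0.96/0.94 and 0.82 with one two-look power for the chosen test and arms. At 180/360 this is about 0.93 pooled (0.91 with 10% drop-out) or about 0.90 for the unadjusted logistic Wald test (0.85 with drop-out). At 180/90 it is about 0.76 pooled or 0.70 logistic Wald.

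**Cost.** SAP wording only. At 180/360 the pooled Z gives up about 2 points of power against the unpooled Z (0.952 to 0.930), makes an interim stop under the planned effect less likely (48% to 21%), and leaves a less favourable stated power than 0.96. If 180/90 is the true allocation, the change exposes a power shortfall that wording cannot repair.

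### The written 1:2 randomization ratio is the reverse of the 180/360 arm targets, and the overall power of 0.82 does not follow from the inputs and method behind 0.96 and 0.94

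*Combined protocol and SAP*

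**What the plan says.** Allocation. The Randomization section states "Patients will be randomized in ratio of 1 (control):2 (intervention) stratified by site of primary care", "with random block sizes of 3 or 6". The same paragraph gives an accrual goal, "our goal is to enroll 5 patients to TeleGRACE each month", and a three-year target of "180 patients to TeleGRACE and 360 to usual care". The Enrollment part of Data Monitoring also uses 180 as its target.

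Power. The Power section assumes 90-day mortality of 2% on TeleGRACE and 8% on usual care with a one-sided normal test at 0.05. It states "With 180 TeleGRACE and 360 usual care patients, the study has 0.96 power at detect the efficacy of TeleGRACE program" and then "Considering a 10% drop-out, the analysis has 0.94 power to establish the TeleGRACE efficacy with the same effect size".

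Interim. The Interim Analysis section plans one O'Brien-Fleming look when half of the patients can be evaluated, with bounds -2.54 and -1.66 and overall error 0.05. It ends with "The overall power with the interim analysis for this study is 0.82". It gives no arm sizes, event rates or drop-out for that figure. Its hypotheses compare the 90-day mortality proportions p1 and p2. The Intention-to-Treat section describes the primary comparison as "adjusting for the baseline characteristics that are significantly different by logistic regression for the binary outcome".

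**The concern.** One control to two intervention patients cannot produce 180 TeleGRACE and 360 usual care patients; those targets need two controls to one intervention patient. A reader cannot tell from the text which allocation the list implements.

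The fall from 0.96 or 0.94 to 0.82 is presented beside the interim look, as if the look caused it. A single O'Brien-Fleming look at half the information costs almost no power, so another difference in inputs or method must lie behind the figure, and the plan does not state one.

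The two matters are linked because every power figure depends on the arm sizes. If only 0.82 were corrected and the list turned out to follow the written ratio, 0.96 and 0.94 would remain in the plan and would be wrong.

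**Working it through.** **Allocation.** 5 per month × 36 months = 180, which agrees with 180 in the TeleGRACE arm. 360/180 = 2 controls per intervention patient, the reverse of the written ratio. Blocks of 3 or 6 fit either direction. The written ratio with 180 TeleGRACE patients would imply 180/2 = 90 controls, a number stated nowhere.

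**Inputs.** Rates 0.02 and 0.08, so d = 0.06; one-sided 0.05 (z = 1.645); arms 180/360, or 162/324 after 10% loss; bounds 2.54 and 1.66 in absolute value; look at half of each arm, so the two statistics correlate √0.5.

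**Reproducing 0.96 and 0.94.** Unpooled SE = √(0.02×0.98/n_T + 0.08×0.92/n_C); power = Φ(d/SE − 1.645).

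- 180/360: SE = 0.01770, d/SE = 3.390, power = Φ(1.745) = 0.9595.
- 162/324: SE = 0.01866, d/SE = 3.216, power = Φ(1.571) = 0.9419.

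Both match the Power section.

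**Checking the bounds.** Under the null, 1 − P(Z1 < 2.54, Z2 < 1.66) = 0.0502, consistent with 0.05.

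**Adding the look by the same method.** Overall power cannot be less than the chance of crossing at the final analysis alone: Φ(3.390 − 1.66) = 0.958 at 180/360 and Φ(3.216 − 1.66) = 0.940 at 162/324. The exact bivariate normal calculation at 180/360 has limits 2.54 − 3.390×√0.5 = 0.143 and 1.66 − 3.390 = −1.730, and gives 0.959. At 162/324 it gives 0.941. The gaps to 0.82 are 0.139 and 0.121.

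**Overall power with the look under other readings.** Pooled means the pooled SE sets the threshold and the unpooled SE the spread. Null-pooled means the pooled SE is used for both.

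| TeleGRACE/control | Unpooled | Pooled | Null-pooled |
|---|---|---|---|
| 180/360 | 0.959 | 0.913 | 0.867 |
| 162/324 | 0.941 | 0.882 | 0.835 |
| 360/180 | 0.872 | 0.922 | 0.956 |
| 324/162 | 0.839 | 0.900 | 0.937 |
| 180/90 (implied, not stated) | 0.625 | 0.729 | 0.764 |

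Other routes near 0.82:

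- Log-odds-ratio Wald at 180/360: ln OR = 1.449, SE = 0.567, ratio 2.558; 0.817 with the look.
- Null-pooled with continuity correction at 180/360: 0.821.
- Pooled with continuity correction at 162/324: 0.825.
- Unpooled with continuity correction at 360/180: 0.826.

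None of these, nor the 0.835 and 0.839 in the table, comes from a convention that also gives 0.96 and 0.94. For example, the log-odds-ratio formula without a look gives 0.819 at 180/360 and 0.783 at 162/324. Only one other risk-difference form tried matches both published figures, null-pooled with the arms swapped (0.9563 and 0.9379), and with the look it gives 0.956 and 0.937.

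**Simulation** (1,000,000 trials per case, stated bounds, 2% versus 8%). Overall power at 180/360 is 0.952 with an unpooled Z and 0.930 with a pooled Z. With both arms at a common rate between 5% and 8%, overall one-sided error at 180:360 is 6.6–7.2% unpooled and 4.5–4.7% pooled.

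**The case against.** The strongest reply on power is that 0.82 may be the correct output of a different and more conservative formula. The log-odds-ratio Wald calculation uses exactly 180/360, 2% versus 8% and the stated bounds, needs no drop-out or continuity correction, and gives 0.817. The primary analysis is a logistic regression, so this is a natural candidate. That stands. A reader might infer that 0.82 was computed from different arm sizes or rates, or that it is a plain reporting error. The documents support neither inference, because they give no inputs for the figure and the same inputs with another method can produce it. What survives is that 0.82 and 0.96/0.94 are not on the same combined basis of inputs and method, and that the look does not explain the gap.

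On allocation, 180/360 is stated outright twice, and the accrual rate and monitoring target both agree with 180 TeleGRACE; the opposite direction rests on one phrase. Transposed labels are therefore the simplest explanation. A reader might infer that the trial will have 90 controls and power of 0.63 to 0.76. That is conditional on a control number that the plan never gives.

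A reader might also infer that the interim test is wholly unspecified. It is not: the hypotheses on p1 and p2 and the reference to normal testing point to a two-proportion Z. What is missing is the variance form and the link to the adjusted logistic model.

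**Conclusion.** Both inconsistencies are real. The written ratio contradicts the arm targets, and 0.82 lies 12 to 14 points below what the inputs and method behind 0.96 and 0.94 give once the stated bounds are added. The cause of 0.82 is unknown.

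This does not show an underpowered trial. If 180/360 stands, the two-proportion formulas without continuity correction put overall power above 0.82 (0.867 to 0.959), and the bounds hold 0.05 under the normal model. The exposure is conditional: if the list follows the written ratio with 180 TeleGRACE patients, power is about 0.63 to 0.76 and the Power section's figures fall as well.

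The results assume 2% and 8% mortality, a look at exactly half of each arm, and unadjusted tests. The point should be fixed but does not call for a redesign.

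**What to change.** 1. Check the randomization list in use and make the ratio and the arm targets in the Randomization section agree with it.
2. Restate all three powers from one stated set of arm sizes, event rates, drop-out, bounds and test form. If 180/360 stands, overall power is 0.96 by the unpooled formula (0.952 simulated) or 0.91 by the pooled formula (0.930 simulated). If the written ratio governs, recompute 0.96 and 0.94 too.
3. Name the Z statistic and variance form compared with -2.54 and -1.66 at each look, and say how it relates to the adjusted logistic regression. At 180:360 the pooled form is preferable, because its simulated error stays below 5% at common rates of 5–8% while the unpooled form exceeds it.

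The cost is SAP wording and a short recalculation; the bounds need no change under the normal model. The downside of the pooled form is that the fixed-design figures of 0.96 and 0.94 become about 0.92 and 0.89 (pooled formula: 0.9154 and 0.8851).
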